ABL: accidental bowel leakage **AE:** adverse event **BM**: bowel movement **CDI:** Clostridium difficile infection **CRF**: case report form CTCAE: common terminology criteria for adverse events **DSMB:** Data Safety Monitoring Board FDA: Food and Drug Administration FDI-20: Pelvic Floor Disability Index FI: fecal incontinence FIQL: Fecal Incontinence quality of life FMT: Fecal Microbiota Transplantation GCP: good clinical practices HIPPA: Health Insurance Portability and Accountability Act of 1996 **IBS**: irritable bowel syndrome **ICH:** International Conference on Harmonisation **IRB**: Institutional Review Board MDRO: multi-drug resistant organism NG: nasogastric NGT: nasogastric tube **NIH:** National Institutes of Health **OCR**: Office of Clinical Research **OHRP**: Office for Human Research Protection PGSC: Patient Global Symptom Control PHI: protected health information **PI**: principal investigator **PMT:** Penn Microbiome Therapy QOL: quality of life **RCT**: randomized clinical trial **R-CDI**: recurrent *Clostridium dificile* infection SAE: serious adverse event **SoA**: schedule of activities SUSAR: suspected unexpected serious adverse reaction **UP**: unanticipated problems

1 STUDY SUMMARY

1.1 Synopsis Title: Fecal Microbial Transplantation (FMT) For the Treatment of Fecal Incontinence in Women FMT for FI **Short Title:** Open label pilot study assessing FMT to treat fecal incontinence in Study women > 50 years of age. **Description: Objectives:** The primary objective is to determine if fecal microbial transplantation leads to clinical improvement in fecal incontinence. Change in the St. Mark's Vaizey score, a measure of fecal incontinence Primary severity, 4 weeks after FMT. **Endpoint:** Secondary Determine whether the effectiveness of microbial engraftment following **Endpoints:** fecal microbial transplantation is associated with the degree of clinical improvement. Determine whether the baseline microbiota configuration affects engraftment in fecal microbial transplantation for fecal incontinence. Our working hypothesis is that the transplant will be more effective in baseline samples with lower microbial diversity. 15 evaluable women, > 50 years of age, who have been diagnosed with Study **Population:** fecal incontinence and have failed standard treatment. 1/2Phase: **Description of** Penn Medicine - University of Pennsylvania Health System Sites/Facilities Participants will be enrolled form the Urogynecology clinics at the Enrolling University of Pennsylvania. **Participants: Description of** Participants will undergo fecal microbial transplantation (FMT) using the Penn Microbiome Therapy – 002 (PMT-002): no more than 152 mL Study **Intervention:** suspension for intragastric or intraduodenal administration from 40g human stool, comprising $1 \times 10^8 - 1 \times 10^{12}$ anaerobic bacterial CFUs/dose. **Study Duration:** 24 months **Participant** Approximately 8 months **Duration:**

1.2 Schema

Screening/Enrollment Week 12 (+/- 7 days) (80 days (+/- 7 days) Follow-Up: 30 & 60 minutes Treatment Visit 1 (within 30 days of screening *) Phone Contact # 1 (within 7 days of treatment) Week 4 (+/- 7 days) Phone Contact # 2 Study Visit 2 Study Visit 3 Procedures Informed Consent Х Demographics Х Medical History Х **Concomitant Medication** Х Х Х Х Х Х Review Abbreviated Physical Х X** X** X** Stool Collection PFIQ-7 Х Х Х Х Adaption Index Х Х Х **Dietary Screener** SF-12 Х Х Х PFDI-20 Х Х Х Pregnancy Test (women of Х Х Х Х childbearing potential) ABLe Questionnaire Х Х Х Radiologic/Imaging Х Assessment FIOL Х Х Х Bristol Stool Index Х Х Х Questionnaire St. Mark's Score Х* Х Х PMT Administration Х Vital Signs Review Х Х Symptom Review PGI-I Х Х Х PGSC Х Х Х **AE/SAE** Review Х Х Х Х Х Х Х Х Х Х Х Protocol Deviation Review Х

1.3 Schedule of Activities (SoA)

Page 8 of 42

Procedures	< Screening/Enrollment	Treatment Visit 1 (within 30 days of screening *)	Follow-Up: 30 & 60 minutes	Phone Contact # 1 (within 7 days of treatment)	<pre>c Study Visit 2 Week 4 (+/- 7 days)</pre>	<pre>c Study Visit 3 Week 12 (+/- 7 days)</pre>	Phone Contact # 2 180 days (+/- 7 days)
Temperature Log	X				X	X	
Completion One Week BM Diary		X		X	X		
 * If time between screening and visit one is greater than 30 days, this test must be repeated prior to administration of FMT. ** Stool Collection will be performed by self-collection procedures and brought by the patient on day of study visit or mailed. 							

2 INTRODUCTION AND RATIONAL

2.1 Study Rationale

Fecal incontinence, also known as accidental bowel leakage, is a common condition that is an immense burden to older women, caregivers, and the health care system. Traditionally, fecal incontinence has been ascribed to obstetric neuromuscular injury, but preliminary results of a Penn led translational study in the Pelvic Floor Disorders Network show that gut microbiota may be a significant contributor (Arya et al., Neuro Uro, 2018). The overall goal of this study is to gather pilot data in order to conduct a future randomized controlled trial (RCT) for a novel treatment for fecal incontinence in older women utilizing fecal microbial transplantation (FMT). Our hypothesis is that infusion of intestinal microbiota from healthy donors to older women with fecal incontinence will increase microbial diversity, reduce symptom severity, and improve quality of life. We plan to conduct a single arm open label clinical trial of FMT for the treatment of fecal incontinence refractory to conservative management. We will measure the impact of FMT on change in symptom severity and quality of life and stool microbial diversity at 4 and 12 weeks after FMT.

2.2 Background

Childbirth and its associated neuromuscular injury to the anal sphincter muscles have traditionally been considered as the cause of fecal incontinence in women. However, the onset of fecal incontinence is usually after age 50 which is remote from delivery (Robinson, FPMRS, 2013; Rey, Am J Gastro, 2019). Recent large epidemiologic studies suggest that gut motility (diarrhea) and stool consistency (liquid stool) are significant contributing factors that are more important than obstetric factors in the pathogenesis of fecal incontinence (Robinson, FPMRS, 2013; Rey, Am J Gastro, 2019; Bharucha, Gastroenterology, 2010). Since gut motility and stool consistency are modulated by gut microbes, Penn investigators are currently performing a large multi-center translational study using 16S rRNA gene sequencing to investigate stool microbiota and metabolites in women with fecal incontinence and controls. The hypothesis of this study is that fecal incontinence is caused by abnormalities of gut microbial pathways that synthesize butyrate, a metabolite known to modulate gut motility and consistency.

The Penn led study has yielded promising results. *Fecalibacterium prausnitzii*, an important producer of gut butyrate, is lower in women with fecal incontinence than controls. Additionally, functional profiling of the microbial metagenome has revealed that at least four additional pathways may be involved in fecal incontinence (Arya, Neuro Uro, 2018; unpublished data). Thus, gut dysbiosis, involving a variety of microbiota and metabolites, may be important contributors to fecal incontinence and restoring normal fecal microbiota could be a potential novel way of treating fecal incontinence.

Possible options for treating gut dysbiosis include dietary manipulation, probiotics, prebiotics, and FMT. Human feces from healthy donors is diverse and contains many more types of

microbiota than pro- or prebiotics. FMT is also emerging as a promising treatment for inflammatory bowel disease and irritable bowel syndrome (Parfenov, Ter Arkh, 2018; Narula, Inflamm Bowel Dis, 2017; Shi Y, PLoS One, 2016; Holleran, Drugs Today, 2018; Halkjaer, Gut, 2018; Arya, Neuro Uro, 2018). The principal of restoration of dysbiotic gut microbiota through FMT could be applied as a treatment to reduce the severity of fecal incontinence and potentially even remission of disease. Thus, we aim to test the efficacy of FMT for the treatment of fecal incontinence in women.

2.2.1 Assessment for Potential Study Products Drug-Drug Interactions

Potential interaction between the study product and other drug products is currently unknown. As this information is unknown, individuals who are immunocompromised have been excluded from this protocol. Additionally, individuals who have chronic antibiotic use are excluded as investigators are currently unsure if this could potentially be a confounding variable.

2.2.2 Clinical Adverse Event Profile

Based on the published literature for the use of FMT in other disease states, it is expected that gastrointestinal symptoms (including fever, aspiration, belching, bloating, nausea or vomiting, gastroesophageal reflux, abdominal cramps, abdominal pain, diarrhea, constipation) may be common post administration of the investigational products, both as a consequence of the underlying disease being treated, and potentially as an adverse effect of the administered product (Halkjaer, Gut, 2018; Johnsen, Lancet, 2018; Table 1).

To distinguish a causal relationship between these adverse effects (AEs) and the investigational product, we will set a threshold of \geq 50% increase in gastrointestinal symptom severity (e.g., number of stools or volume of diarrhea; number of vomiting episodes or hours/day of nausea) as compared to symptom severity in the one week period surrounding the intervention.

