3 STUDY OBJECTIVES AND ENDPOINTS

OBJECTIVES	ENDPOINTS
Primary	
Determine if fecal microbial transplantation leads to clinical improvement in refractory fecal incontinence in older women.	Number of subjects that show significant improvement at 4 weeks after FMT, and will be maintained at 12 weeks, relative to baseline using the St. Mark's Vaizey score, a measure of fecal incontinence severity.
Primary Safety	
Determine the safety of FMT administration via naso-gastric tube in older women with FI.	Frequency of adverse events, serious adverse events, and adverse events of special interest (including allergic reaction and gastrointestinal symptoms).
Secondary	
Determine if FMT leads to improved quality of life for subjects.	Number of subjects that have an improved quality of life at 4 and 12 weeks, measured by the FIQL scale.
Determine if the effectiveness of microbial engraftment following fecal microbial transplantation is associated with the degree of clinical improvement.	Concentration of microbiota present at baseline vs. at week 4 and at 12 weeks (optional)in subjects that demonstrate a significant improvement at 4 weeks after FMT, relative to baseline using the St. Mark's Vaizey score.
Tertiary	
Determine whether the baseline microbiota of the subject affects engraftment in fecal microbial transplantation for fecal incontinence.	Concentration of microbiota at baseline vs. concentration of microbiota at 4 weeks and at 12 weeks (optional).

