8.3 Adverse Events and Serious Adverse Events

8.3.1 Definition of Adverse Events (AE)

An adverse event (AE) is any untoward medical occurrence associated with the use of a drug in humans, whether or not considered drug related. Intercurrent illnesses or injuries should be regarded as adverse events.

A pre-existing condition should be recorded as an adverse event if the frequency, intensity, or the character of the condition changes.

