8.3.3.2 Relationship to Study Intervention

All adverse events (AEs) must have their relationship to study intervention assessed by the clinician who examines and evaluates the participant based on temporal relationship and his/her clinical judgment. The degree of certainty about causality will be graded using the categories below. In a clinical trial, the study product must always be considered.

• Definitely Related – There is clear evidence to suggest a causal relationship, and other possible contributing factors can be ruled out. The clinical event, including an abnormal laboratory test result, occurs in a plausible time relationship to study intervention administration and cannot be explained by concurrent disease or other drugs or chemicals.

• Probably Related – There is evidence to suggest a causal relationship, and the influence of other factors is unlikely. The clinical event, including an abnormal laboratory test result, occurs within a reasonable time after administration of the study intervention, is unlikely to be attributed to concurrent disease or other drugs or chemicals, and follows a clinically reasonable response on withdrawal (de-challenge). Re-challenge information is not required to fulfill this definition.

• Potentially Related – There is some evidence to suggest a causal relationship (e.g., the event occurred within a reasonable time after administration of the trial medication). However, other factors may have contributed to the event (e.g., the participant's clinical condition, other concomitant events). Although an AE may rate only as "possibly related" soon after discovery, it can be flagged as requiring more information and later be upgraded to "probably related" or "definitely related", as appropriate.

• Unlikely to be related – A clinical event, including an abnormal laboratory test result, whose temporal relationship to study intervention administration makes a causal relationship improbable (e.g., the event did not occur within a reasonable time after administration of the study intervention) and in which other drugs or chemicals or underlying disease provides plausible explanations (e.g., the participant's clinical condition, other concomitant treatments).

• Not Related – The AE is completely independent of study intervention administration, and/or evidence exists that the event is definitely related to another etiology. Note: there must be an alternative, definitive etiology documented by the clinician.

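### The 50% increase rule in section 2.2.2 cannot separate a product effect from ordinary week-to-week variation in a single-arm trial, and it conflicts with the relatedness grading in 8.3.3.2 and 8.3.5

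*Combined protocol and SAP*

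**What the plan says.** Section 2.2.2 expects "gastrointestinal symptoms (including fever, aspiration, belching, bloating, nausea or vomiting, gastroesophageal reflux, abdominal cramps, abdominal pain, diarrhea, constipation" to be common after dosing, partly because of the underlying disease. It then states: "To distinguish a causal relationship between these adverse effects (AEs) and the investigational product, we will set a threshold of" at least a "50% increase in gastrointestinal symptom severity (e.g., number of stools or volume of diarrhea; number of vomiting episodes or hours/day of nausea"). It gives no minimum absolute change, no handling of a zero reference, no rule for combining symptoms and no variability data. The reference for the increase is worded only "as compared to symptom severity in the one week period surrounding the intervention".

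Section 8.3.3.2 says that all adverse events "must have their relationship to study intervention assessed by the clinician who examines and evaluates the participant based on temporal relationship" and clinical judgement, in five categories. Section 8.3.5 asks again whether each event is related. Neither mentions the 50% threshold.

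The primary safety endpoint in section 3 is "Frequency of adverse events, serious adverse events, and adverse events of special interest (including allergic reaction and gastrointestinal symptoms"), with no relatedness condition. Section 9.4.1 summarises safety descriptively. Section 8.3.1 adds a recording rule: "A pre-existing condition should be recorded as an adverse event if the frequency, intensity, or the character of the condition changes".

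**The concern.** The sentence in 2.2.2 claims to do what a control arm normally does, namely tell product harm from background symptoms. A ratio of two short counts is a poor instrument for that. A rise from 1 to 2 episodes or from 2 to 3 meets it. After a week with none, a single episode is either an unlimited increase or an undefined one. The trial is single-arm and unblinded, so it cannot show how often the rule is met without any product effect.

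There are also two methods for one judgement. The same event could be causal under 2.2.2 and unlikely to be related under 8.3.3.2. Safety is a primary objective and the trial is meant to inform a later randomised study. A statement that some number of women had gastrointestinal symptoms caused by FMT would therefore carry weight, and its basis should be sound.

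**Working it through.** **Inputs from the documents.** Threshold: at least 1.5 times the reference (2.2.2). Symptom entries: ten, counting nausea or vomiting once (2.2.2). Sample size: 15 women (9.3). Controls: none (4.1). The plan states no error rate for the rule, so there is no figure to reproduce.

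**Assumptions.** The documents give no weekly symptom rates or variances. I take a reference-week count B and a later-week count A as independent Poisson draws and vary the mean. The text does not define the reference week clearly; I assume a clean pre-dose week.

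**One symptom.** With a zero reference followed by any episode counted as an increase:

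p = P(B=0)·P(A≥1) + Σ over b≥1 of P(B=b)·P(A≥1.5b)

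At mean 2 with no effect, the terms for b = 0 to 4 are:

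- b=0: 0.1353 × 0.8647 = 0.1170
- b=1: 0.2707 × 0.5940 = 0.1608
- b=2: 0.2707 × 0.3233 = 0.0875
- b=3: 0.1804 × 0.0527 = 0.0095
- b=4: 0.0902 × 0.0166 = 0.0015

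The sum is 0.376; later terms are negligible. The same calculation at other means, and with the later mean raised by half:

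| Mean per week | No effect, zero counted | No effect, zero dropped | True 50% rise, zero counted |
|---|---|---|---|
| 1 | 34% | 11% | 48% |
| 2 | 38% | 26% | 54% |
| 5 | 29% | 29% | 53% |
| 14 | 16% | 16% | 52% |

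At 2 per week, 15 × 0.376 = 5.6 women would be flagged on that symptom with no effect, and 15 × 0.543 = 8.1 with a true 50% rise. Discrimination improves at higher counts if they are Poisson. With more week-to-week spread, the no-effect figure at 14 per week rises to 26% (negative binomial, k=10) or 37% (k=2).

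**At least one of ten symptoms, no effect.** Under independence this is 1−(1−p)^10.

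- Zero counted: 17.8% at 0.02 per week, 59.5% at 0.1, 98.5% at 1, 99.1% at 2, 82.0% at 14.
- Zero dropped: 0.4% at 0.1 per week, 25.1% at 0.5, 69.6% at 1, 95.0% at 2.
- Correlated symptoms, zero counted, correlation 0.3, 0.6 and 0.9: 89.5%, 76.4% and 56.6% at 1 per week; 46.2%, 32.6% and 18.8% at 0.1.
- Shared patient factor, zero counted: 32% at 0.05 per week and 47% at 0.1. Zero dropped: under 2% at both.

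The result does not need ten symptoms. Three independent symptoms at 2 per week give 1−(1−0.376)³ = 76%, or 1−(1−0.259)³ = 59% with zeros dropped.

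**Is there a reference to divide by?** Section 8.1.1 sends women home before dosing with a one-week bowel movement diary and mentions no adverse event card. The card is described with the second diary (8.1.2.1) and the final diary (8.1.4). Sections 8.2 and 8.3.5 place the card in the study diary without saying which one. Belching, bloating, reflux or cramps may therefore have no recorded pre-dose week. If so, either any later episode counts as an increase, or a new symptom can never meet the rule.

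**The case against.** The strongest objection concerns scope. The threshold stands in a background section and is not cited again. The safety endpoint counts events whatever their cause, the analysis is descriptive, and events of special interest are defined by grade. One pause criterion in 8.3.8 does depend on relatedness (two or more subjects with a related serious event), but it does not refer to the 50% rule. All of this stands. The threshold is also not the plan's only means of attribution, since 8.3.3.2 and 8.3.5 grade every event.

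A second objection is that the ten entries are not interchangeable weekly counts. Fever is followed on a temperature log, and the severity examples include volume and hours per day. This also stands. It is one reason why the any-of-ten figures are only illustrative and the single-symptom figures carry the argument.

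Two stronger readings are tempting. A reader might infer that the rule will fire in most women even if FMT does nothing. The documents do not support that as fact: they give no rates, and the figure falls below half for rare or highly correlated symptoms, and much lower for rare ones if zero references are dropped. A reader might also infer from 8.3.1 that improvement in incontinence would be recorded as an adverse event, because that rule gives no direction of change. But 8.3.1 first requires an untoward occurrence, which improvement is not.

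**Conclusion.** The concern holds in limited form. As written, a 50% increase cannot distinguish a causal relationship. For a single low-count symptom it is met by chance in roughly a third of women (34% at 1 per week, 38% at 2), and at 2 per week it is met in only 54% when there is a true 50% rise. These figures rest on equal Poisson means, a clean pre-dose week and counting a zero reference followed by any episode.

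The chance of at least one flag per woman depends on the assumptions: under 20% to 99% with zero references counted, and close to nil for rare symptoms with them dropped. Most women being flagged is possible but not established.

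The conflict between 2.2.2 and the grading in 8.3.3.2 and 8.3.5 is on the page and needs no assumption. The effect falls on any statement about product-related gastrointestinal events. It does not fall on the adverse event counts or, as written, on the pause rules.

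**What to change.** In 2.2.2, remove the claim that a 50% increase distinguishes causality, and reconcile the section with 8.3.3.2 and 8.3.5 so that one relatedness method applies. If the 50% figure is kept, use it only as a descriptive flag with a minimum absolute increase stated in advance.

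For each measure recorded in both the pre-dose and post-dose diaries, report the paired weekly difference across the women with a 95% interval, and label it uncontrolled pre-post change. It has no control either, so it describes and does not attribute. Report symptoms with no pre-dose record as incidence only.

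As a minor clarification in 8.3.1, replace *changes* with *worsens*. A stricter standard, such as worsening beyond usual variation, could not be measured from one pre-dose week.

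The cost is wording in a few sections and one table from diaries already planned, with no new visits or participants. The downside is that the plan would no longer have a single yes/no causal threshold.

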8 STUDY ASSESSMENT AND PROCEDURES

8.1 Efficacy Assessments

8.1.1 Screening Visit

Potential candidates will be evaluated for eligibility per sections 6.1 and 6.2 and written informed consent will be obtained. Consented participants will be required to complete the following forms during their Baseline visit:

- Consent
- Eligibility Check List (includes St. Mark's Vaizey questionnaire)
- Pregnancy Test (if childbearing age)

If eligible, the following will be completed:

• Dietary Screener

• Questionnaires (Demographics, Medical History, SF-12, PFDI-20, ABLe Questionnaire, FIQL, Bristol Stool Index, PFIQ-7, Adaptation Index, PACSYM)

- Abbreviated Physical Exam
- Medication Log

Subjects will also be required to take the following home to complete prior to their treatment visit.

- One-week BM diary
- Stool Collection Kit (see stand-alone collection instructions)

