8.1.2 Visit 1: Treatment

At this visit, the study coordinator will collect the one-week BM diary and stool sample from the subject. The PI or another trained physician will meet with the patient. Vital signs will be done to document temperature, blood pressure, heart rate, and oxygen saturation. A nasogastric tube will be placed and secured. The subject will then be escorted to the radiology suite by the study coordinator. A chest x-ray will be performed to ensure adequate placement of the nasogastric tube. The PI or trained physician will confirm adequate placement of the tube with the attending radiologist. The subject will then be escorted back to the office suite by the study coordinator. The PI or trained physician will then administer the treatment. The PMT-002 product will be drawn into a syringe and the syringe will be connected to the nasogastric tube (NGT) and the product will be pushed into the tube until all of the FMT product is administered. The NGT will then be removed by the PI or trained physician. The subject will remain in the office for one hour following the administration of the PMT product.

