8.1.4 Visit 2 (4 weeks post treatment)

Subjects will come to the office for a visit 4 weeks (\pm 7 days) after administration of the FMT treatment or be conducted by telemedicine or telephone.

During their first follow-up visit, the subjects will return to the clinical site in person or via mail:

- Second one-week bowel movement (BM) diary
- Temperature and Adverse Events log form
- Stool specimen

During the visit, the following forms will be completed:

- Medication Log
- Adaption Index
- SF-12
- PFDI-20 (Pelvic Floor Disability Index)
- ABLe Questionnaire
- FIQL (Fecal Incontinence quality of life)
- Bristol Stool Index
- St. Mark's Score
- PGSC (Patient Global Symptom Control)

- Global Impression Improvement
- PACSYM
- PFIQ-7
- AE/SAEs

Subjects will be sent home with a final one-week BM diary that they will return during their 12week visit. The diary will include a card for the collection of all solicited adverse events. Subjects will also be sent home with a stool collection kit to be returned at the 12-week visit or be returned by mail if a telemedicine or telephone visit (optional).

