8.3.4 Adverse Events of Special Interest

Any gastrointestinal symptom or allergic reaction adverse event grade 3 or higher will be classified as an adverse event of special interest. These events may be related to the use of the FMT product and should be recorded as an adverse event of special interest and reported to the sponsor. Reporting of Adverse Events of Special Interest should follow the reporting pathway described for Serious Adverse Events.

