8.3.8 Stopping/Halting Rules

A study wide pause of PMT administration will be instituted if one of the following occur:

- Death attributable to FMT
- Suspected transmission of infection from donor to patient
- If two (2) or more subjects experience the same Grade 3 or higher AE
- If two (2) or more subjects experience an SAE related to the study product
- There is an increase in frequency of long-term adverse events (e.g., IBD, metabolic disease) in > two (2) FMT treatment subjects

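### The 50% rule in section 2.2.2 for attributing GI symptoms to FMT uses a reference week that, as written, includes days after FMT, so it can miss a true doubling.

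*Combined protocol and SAP*

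**What the plan says.** Section 2.2.2 notes that GI symptoms after dosing may come from the underlying disease or from the product. It then gives a numerical rule for telling the two apart: "To distinguish a causal relationship between these adverse effects (AEs) and the investigational product, we will set a threshold of" a 50% or greater increase in severity, "as compared to symptom severity in the one week period surrounding the intervention". Its examples are stool number, diarrhea volume, vomiting episodes and daily hours of nausea. It does not say how many days of the week lie on each side of the dose, and no other section defines the reference.

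A pre-treatment record does exist. Section 8.1.1 lists a one-week BM diary among the items for home: "Subjects will also be required to take the following home to complete prior to their treatment visit". At Visit 1 (8.1.2), "the study coordinator will collect the one-week BM diary and stool sample from the subject". Section 2.2.2 does not name this diary as the reference.

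Section 8.3.3.2 gives a separate route to causality. Relatedness of every AE is "assessed by the clinician who examines and evaluates the participant based on temporal relationship and his/her clinical judgment". It does not mention the 50% rule, and 2.2.2 does not mention 8.3.3.2.

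**The concern.** A reference for detecting harm should not contain the exposure. A week *surrounding* the dose covers days on both sides of it. If FMT raises stool frequency at once, those raised days enter the comparator and the measured increase shrinks. The same days also fall in the 7-day period after dosing in which 8.3.3.3 asks for close monitoring of GI symptoms.

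The error runs in one direction, toward not attributing a worsening to FMT, and it is greatest for worsening that begins at the dose. These women have bowel symptoms at entry. Diarrhea is both a listed risk of FMT (2.3.1) and a named contributor to fecal incontinence (2.2), so separating product from disease is the purpose of the rule. At stake is whether the plan's one numerical causality threshold does what 2.2.2 says it is for, in a pilot meant to supply safety data for a later randomized trial (4.1).

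**Working it through.** The 50% is a chosen cut-off, so there is no figure of the plan's own to reproduce. The check is what the rule does to a known change.

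**Inputs from the protocol (2.2.2).** The rule is met when post-FMT severity divided by reference severity is at least 1.5. The reference is one week, that is 7 days. Stool number is one of the named measures.

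**Assumptions not in the documents.** Of the 7 reference days, *m* fall after FMT. The rise starts at the dose and is sustained. The pre-FMT daily rate is *b* and the post-FMT daily rate is *r·b*.

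**Formulas.**

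- Reference daily mean = *b*[(7 − *m*) + *m·r*]/7.
- Observed ratio = 7*r*/[(7 − *m*) + *m·r*].
- Setting this to at least 1.5 gives *r* ≥ 1.5(7 − *m*)/(7 − 1.5*m*), provided 7 − 1.5*m* > 0, that is *m* < 4.67. For larger *m* no rise is big enough.

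The rate *b* cancels. Because the rise is constant, the ratio is the same whether post-FMT severity is taken by day or as a weekly mean.

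**Results.**

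| Post-FMT days in the reference week | True doubling reads as | Meets 50%? | True increase needed |
|---|---|---|---|
| 0 | +100% | yes | 50% |
| 1 | 14/8 = 1.75, +75% | yes | 64% |
| 2 | 14/9 = 1.56, +56% | yes | 88% |
| 3 | 14/10 = 1.40, +40% | no | 140% |
| 4 | 14/11 = 1.27, +27% | no | 350% |
| 5 | 14/12 = 1.17, +17% | no | never met |

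A doubling is exactly on the threshold when 14/(7 + *m*) = 1.5, that is *m* = 2.33. A whole-day split therefore fails from 3 days upward.

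**Worked case.** A woman goes from 14 stools a week to 28.

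- Clean reference: 14, so the cut-off is 1.5 × 14 = 21 and 28 meets it.
- Three post-FMT days: reference 4×2 + 3×4 = 20, cut-off 30, and 28 fails.
- Four post-FMT days: reference 3×2 + 4×4 = 22, cut-off 33, and 28 fails.

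**The other side of the trade.** A clean reference also flags more chance fluctuation. I simulated a woman with no true change, assuming 2 stools a day, independent Poisson days, and the post-FMT 7-day total as the quantity compared. She meets the 50% threshold about 16% of the time with a clean week, against 10% with 3 post-FMT days in the reference and 7% with 4.

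**The case against.** The strongest reply is that the rule has little power to do harm. It appears once, in a background section. The operative section, 8.3.3.2, requires a clinician to judge the relatedness of every AE from timing and judgment, and 8.3.5 repeats that for each event. Neither refers to 50%, so an event that misses the threshold need not be graded unrelated. The safety endpoint in section 3 counts AEs, SAEs and AESIs without regard to cause. Section 8.3.1 already makes a change in the frequency or intensity of a pre-existing condition an AE, with no 50% test. In 8.3.4, "Any gastrointestinal symptom or allergic reaction adverse event grade 3 or higher will be classified as an adverse event of special interest", whatever its cause, and the pause for two women with the same grade 3 or higher AE (8.3.8) does not turn on relatedness either. All of this stands, and it sets the limits of the point.

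The authors may also have meant the week before the dose. If so, the fault is in the wording only; but the text does not say it, and site staff will apply the text.

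The numbers are conditional too. With 1 or 2 post-FMT days a doubling still passes, and a rise that begins after the reference week is not diluted at all.

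Three stronger readings are tempting, and the documents do not support them.

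- A reader might infer that the pause in 8.3.8, "If two (2) or more subjects experience an SAE related to the study product", is weakened. No text lets the 50% rule override the clinician's causality assessment of an SAE.
- A reader might infer that a brief early reaction would vanish entirely. That requires comparing a 7-day post-FMT mean, and 2.2.2 does not say which post-FMT quantity is compared. For example, take 2 stools a day before FMT and 6 a day on three post-FMT days inside the reference: the reference is (4×2 + 3×6)/7 = 3.71. Compared by day, 6/3.71 is +62%, which meets the rule.
- A reader might extend the reference to a week on each side of the dose. Section 2.2.2 says one week.

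**Conclusion.** The concern holds in a limited form. As written, the reference week in 2.2.2 takes in post-FMT days, and this raises the true increase needed from 50% to 140% or 350% in a roughly centred week. A sustained doubling is then missed. The result rests on two assumptions that the documents do not settle: at least 3 of the 7 days follow FMT, and the rise begins at the dose and lasts.

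The damage is confined to the threshold itself and to any relatedness label that leans on it. The plan does not say how the threshold and the clinician's judgment fit together, so two assessors could label the same event differently. The safety endpoint and the grade 3 or higher pause are untouched. It is still worth correcting, because a stated rule works against its stated purpose and the data for a clean reference are already being collected.

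**What to change.** In 2.2.2, replace the reference with: *the mean daily value in the one-week diary completed before FMT (8.1.1); no day after FMT enters the reference*. Add one sentence saying that the threshold informs the clinician's assessment under 8.3.3.2 and does not replace it.

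Include the solicited-symptom card in the first diary. Section 8.1.2.1 puts a card in the second diary and 8.1.4 does so for the last ("The diary will include a card for the collection of all solicited adverse events"), but 8.1.1 mentions none for the first. Without it, nausea and vomiting, which 2.2.2 uses as examples, have no diary value from before FMT to compare with.

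The cost is a few sentences and one card in a diary already handed out, with no new visit or test. The price is somewhat more chance flags, as worked above (about 16% against 7% to 10% under those assumptions). That is a further reason to let the threshold inform the clinician's judgment and not decide cause by itself.
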